Prior to surgery, all consecutive patients scheduled for LVAD implantation will be screened for inclusion into the study. If the patient fulfills the inclusion criteria for the study, he/she will be approached and the study will be described. If the patient agrees to participate, he /she will be given written, informed consent for inclusion in the study. Baseline demographic and clinical characteristics of patients, echocardiographic parameters, hemodynamic data from right heart catheterization and blood samples will be collected. These procedures are a part of standard of care procedures, so the patients will not suffer any discomfort or additional cost due to the inclusion in the study. However, patients will be asked to provide additional blood samples for advanced hemostatic assays and panel reactive antibodies. Randomization is done intraoperatively as detailed later. In cases where the patient will not be eligible for inclusion into the study prior to randomization (e.g. if during the heart positioning the patient becomes hemodynamically unstable and the CPB will a priority have to be used), the additionally collected blood samples will be discarded. The operation is initiated by a standard procedure and all postoperative management will be completed according to institution protocols and standard of care medical guidelines.

Randomization will be done with the help of the REDCap (REDCap electronic data capture tools hosted at UTHealth) (36), a software program that contains a randomization module using stratified randomization (by type of LVAD therapy).

The primary hypothesis is that off-pump LVAD surgery compared with on-pump LVAD surgery reduces a composite outcome of right ventricular dysfunction, thrombotic complications and survival in the short term (30 days) and that these benefits are maintained at long term (1 year). The secondary hypothesis is that off-pump LVAD surgery compared with on-pump LVAD surgery reduces OHP leading to lower complement activation and reduced immune allosensitization in the short term (30 days) and at long term (1 year).

Inclusion criteria

- Adult (≥ 18 years of age)
- The patient has had a diagnosis of end stage heart failure, NYHA class III or IV HF for a minimum of 90 days prior to screening.
- The patient has guideline-directed medical therapy according to ACC/AHA/ESC HF guidelines
- The patient has an Interagency Registry for Mechanically Assisted Circulatory Support (INTERMACS) score of 1-3.

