the blood contacting surfaces of device inflow cannula or outflow conduit or grafts. This will be reported via direct visual inspection (documented by a photograph if available) on pump removal or by sending the pump back to manufacturer for evaluation. Any pump explanted for suspected device thrombosis will be sent back to manufacturer for analysis. All pump thrombosis events will be adjudicated by an independent committee, the Research Review Committee which is described below in the Data and Safety Monitoring Section.

- For patients who will **die in the hospital within 30 days**, the cause of death will be confirmed by postmortem examination performed by a pathologist who will be unaware of the study assignments.

Secondary Outcome Measures

1. Need for blood product transfusion within 48-hours post LVAD implantation
2. Operative safety outcomes: incidence of 30-day mortality (from the day of surgery to 30 days [+/- 3 days]), chest tube output in the first post-operative 24 hours, rate of post-operative re-exploration for bleeding
3. Incidence of allosensitization at 30-days, 6-months and 12-months post-LVAD implantation. Allosensitization is defined as calculated panel reactive antibody (cPRA) > 10%.
4. Readmission for heart failure (follow-up 1 year)
5. OHP, overall coagulation potential and overall fibrinolytic potential in the perioperative period
6. Major bleeding defined as an episode of suspected internal or external bleeding that results in one or more of the following: death, re-operation, hospitalization, transfusion of red blood cells according to INTERMACS definition.

Other Outcome Measures

1. Duration of surgery (skin incision to skin closure)
2. Duration of postoperative mechanical ventilation (length of time from intubation until patient is extubated)
3. Length of ICU stay (length of time from ICU admission from surgery until ICU discharge)
4. Length of hospital stay (length of time from surgery to hospital discharge)
5. Incidence of renal dysfunction defined by INTERMACS criteria
6. Incidence of 30-day mortality (from the day of surgery to 30 days [+/- 3 days])
7. Incidence of post-operative mortality within 6 months and 1 year

8. Device-related complications totaled at 30-days, 6-months and 12-months post-LVAD implantation.
9. Duration and amount of intraoperative and postoperative inhaled nitric oxide use

COLLECTION OF BASIC DATA/PATIENT CHARACTERISTICS

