Preparation of buffy coat: Buffy coat will be removed after the first spinning of the centrifuge and decanted into Eppendorf tubes. The remaining packed RBCs in tubes will be stored for later (storage at -80°C).

DETERMINATION OF ALLOANTIBODIES

The measurement and assessment of alloantibodies is now a standard of care test performed on patients scheduled for LVAD surgery. A single-bead antigen assay on the Luminex platform (One Lambda Inc., Canoga Park, CA) is used at the institution. Mean fluorescence intensity (MFI) >4,000 is considered the threshold of clinical significance. Whenever the alloantibodies and panel reactive antibody status (PRAs) are measured, the data will be transferred from the medical record to the case report forms.

Calculated PRA (cPRA) values will be obtained using the United Network of Organ Sharing cPRA calculator. Sensitization will be defined as cPRA >10%. LVAD-associated sensitization will be defined as cPRA >10% documented after LVAD implantation in patients with cPRA <10% before LVAD implantation.

STATISTICAL METHODS

We calculated a sample size of 140 patients (70 in each arm), which will provide 80% power to detect a 30% relative risk reduction for the composite primary outcome at 30 days. The intention-to-treat principle, in which all participants will be included in their assigned treatment groups regardless of actual surgical procedure performed, will guide all analyses.

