Data will be represented as frequency distributions and percentages. Values of continuous variables will be expressed as mean \pm standard deviation and median with interquartile range, as necessary. Continuous variables will be compared using independent samples t-tests or Wilcoxon rank-sum tests, where appropriate. Categorical variables will be compared by means of χ^2 tests or Fischer's exact test, where appropriate. Hemodynamic variables between ON-pump and OFF-pump procedures will be compared with Kruskal-Wallis tests. To analyze changes in echocardiographic and hemodynamic parameters and laboratory values, McNemar matched-pairs tests will be used to compare preoperative values to postoperative values after matching individual patient data. For all analyses, a $p < 0.05$ will be considered statistically significant. Kaplan-Meier analysis will be used to calculate survival along with a log-rank p value when comparing ON-pump and OFF-pump groups. Actuarial survival at 30-days, 6-months and 1-year post-implantation will be calculated by constructing life tables. All data will be analyzed using STATA 15 software (STATA, 2017, College Station, TX).

EXPECTED RESULTS AND IMPORTANCE OF THE STUDY

As LVADs become a more widely used and accepted treatment option for patients with refractory, end-stage heart failure, it will be necessary to further optimize outcomes and reduce the incidence of postoperative complications. We believe that using off-pump LVAD implantation will significantly reduce transfusion requirements, right ventricular dysfunction and alloantibody formation. We expect that in the off-pump group, there will be less exposure to blood products, which will lead to reduced immunosenzitization. If this research finds that off-pump use can decrease the morbidity and mortality in this patient population, it will greatly influence the manner in which these patients are managed. This would reduce hospitalizations and delays in subsequent transplant planning. This would not only be of great benefit to the patient but would significantly decrease health-care costs.

RISK AND BENEFITS

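### Secondary outcome 3, the incidence of allosensitization, has no baseline condition and is not tied to the protocol's own new-onset definition

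*Combined protocol and SAP*

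**What the plan says.** Under Secondary Outcome Measures in the combined protocol and SAP, item 3 is the incidence of allosensitization at 30 days, 6 months and 12 months after implantation. Its definition is "Allosensitization is defined as calculated panel reactive antibody (cPRA) > 10" per cent. It sets no condition on the value before implantation, names no population at risk and gives no cross-reference.

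The section Determination of Alloantibodies gives two definitions:

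- Unconditional: "Sensitization will be defined as cPRA >10" per cent.
- New onset: "LVAD-associated sensitization will be defined as cPRA >10% documented after LVAD implantation in patients with cPRA <10% before LVAD implantation".

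The same section says of the pre-implant test: "The measurement and assessment of alloantibodies is now a standard of care test performed on patients scheduled for LVAD surgery".

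The secondary hypothesis (Study Design and Patients) is that off-pump surgery leads, among other things, to "reduced immune allosensitization in the short term (30 days) and at long term (1 year").

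Statistical Methods applies intention to treat to all analyses: "all participants will be included in their assigned treatment groups regardless of actual surgical procedure performed". For the arm comparison it says "Categorical variables will be compared by means of" chi-square or Fisher tests, with no baseline adjustment. It also plans pre/post comparisons for echocardiographic, hemodynamic and laboratory values: "McNemar matched-pairs tests will be used to compare preoperative values to postoperative values after matching individual patient data".

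**The concern.** The outcome's wording matches the unconditional definition, while its label points to the new-onset one. The term for new-onset sensitization appears nowhere in the outcome list, the hypotheses or Statistical Methods.

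Nothing else settles the matter. No eligibility criterion refers to cPRA or PRA, so patients sensitised before surgery can be randomised. The McNemar tests work within patients and do not bring baseline cPRA into the comparison between arms.

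The choice matters because the hypothesis is about antibodies forming. The background section on immunologic effects argues that fewer transfusions could limit antibody development, and Expected Results speaks of alloantibody formation. Surgical technique cannot have caused antibodies that were there before the operation. Counting them adds events unrelated to that mechanism. In addition, two analysts following this text could report different numerators and denominators, and the choice could be made after the results are known.

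**Working it through.** The plan gives no expected rate, effect size or power for this outcome, so there is no figure of its own to reproduce. The check is the textual comparison above plus an illustration of what the literal definition would do.

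**Inputs**

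- 70 patients per arm (Statistical Methods).
- New-onset risk on-pump, 22%. This is the background section's figure for LVAD recipients and is not specific to on-pump surgery.
- True risk ratio (RR) for new onset: 0.70, the plan's only stated effect size (given for the primary composite), and 0.50, an assumption with no source in the plan.
- Share *s* sensitised at baseline: not in the documents; shown from 0% to 40%.
- Persistence *q*, the proportion of those patients still above 10% after implantation: assumed 1 at first.
- Two-sided 0.05 (the plan does not state sidedness), one time point, no missing samples.

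**Formulas**

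- Literal event rate = *s·q* + (1 − *s*) × new-onset rate.
- Literal risk difference = (1 − *s*) × RD(new onset) + *s* × RD(persistence). With equal persistence the second term is zero and the difference shrinks by the factor (1 − *s*).
- Power = Φ{[|p1 − p2| − 1.96·√(2p̄(1 − p̄)/n)] / √([p1(1 − p1) + p2(1 − p2)]/n)}, with n = 70 per arm for the literal definition and 70(1 − *s*) for new onset.

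**Worked case, *s* = 20%, RR 0.50**

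- Literal rates: on-pump 0.20 + 0.80 × 0.22 = 0.376; off-pump 0.20 + 0.80 × 0.11 = 0.288. Difference 0.088; apparent RR 0.288/0.376 = 0.77.
- Literal power, n = 70: (0.088 − 1.96 × 0.0796)/0.0793 = −0.86, so about 20%.
- New-onset power, n = 56, 0.22 against 0.11: (0.110 − 1.96 × 0.0701)/0.0694 = −0.40, so about 35%.
- Of the on-pump events, 0.20/0.376 = 53% would predate surgery.

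| True RR | Share *s* | Literal rates, on v off | Difference (points) | Apparent RR | Power, literal | Power, new onset |
|---|---|---|---|---|---|---|
| 0.70 | 0% | 22.0% v 15.4% | 6.6 | 0.70 | 17% | 17% |
| 0.70 | 5% | 25.9% v 19.6% | 6.3 | 0.76 | 14% | 16% |
| 0.70 | 20% | 37.6% v 32.3% | 5.3 | 0.86 | 10% | 14% |
| 0.70 | 40% | 53.2% v 49.2% | 4.0 | 0.93 | 7% | 12% |
| 0.50 | 0% | 22.0% v 11.0% | 11.0 | 0.50 | 42% | 42% |
| 0.50 | 5% | 25.9% v 15.5% | 10.5 | 0.60 | 33% | 40% |
| 0.50 | 20% | 37.6% v 28.8% | 8.8 | 0.77 | 20% | 35% |
| 0.50 | 40% | 53.2% v 46.6% | 6.6 | 0.88 | 12% | 27% |

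Exact enumeration at a 20% share (literal v new onset):

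- Chi-square: 20% v 35% (RR 0.50) and 10% v 15% (RR 0.70).
- Fisher: 15% v 26% and 7% v 9%.

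**Where the attenuation stops.** It requires the arm difference in persistence to be smaller than the arm difference in new onset. With *s* = 20%, RR 0.50 and persistence of 1.0 on-pump against 0.8 off-pump, the literal rates are 0.376 and 0.16 + 0.088 = 0.248. The difference is then 12.8 points, and power is 37% literal against 35% new onset.

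**Stratifying instead of restricting.** This was simulated with a Cochran-Mantel-Haenszel test by baseline status in all patients (20,000 runs, *s* = 20%, RR 0.50):

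| Persistence | Stratified, all patients | Unstratified | Restricted to at-risk |
|---|---|---|---|
| 1.0 in both arms | 0.35 | 0.20 | about 0.35 |
| 0.75 in both arms | 0.27 | 0.22 | about 0.35 |
| 1.0 on-pump, 0.8 off-pump | 0.56 to 0.57 | 0.37 (closed form) | about 0.35 |

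Under no effect the tests rejected in 4.8% to 5.2% of runs.

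**The case against.** The best defence is that the protocol already means new onset. An incidence ordinarily counts new cases, the alloantibody section supplies a matching definition that has no other evident use, and the background speaks of antibodies developing. On that reading nothing is diluted and a cross-reference is all that is needed. This is a plausible account of the intent, and it limits the weight of the point. It does not remove it, because the outcome carries its own definition and that definition agrees with the unconditional one.

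A second defence is that the intention-to-treat sentence governs which arm a patient is counted in and does not clearly forbid an at-risk denominator. The tests, too, are listed generically and none is assigned to this outcome. That is fair: an unadjusted comparison of all randomised patients is the default reading of the text, not a plan stated for outcome 3.

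Third, the size rests on assumptions and is small at a risk ratio of 0.70. This also stands.

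A reader might go further and infer that the endpoint favours one arm or produces false positives. The documents do not support that. Allocation is 1:1 and randomised, so baseline sensitisation is balanced in expectation, and rejection under no effect stayed near 5%. Nor can a reader conclude that sensitised status in all patients is the wrong question. It bears on later transplantation, which the background section itself raises.

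**Conclusion.** The point holds as an endpoint whose definition is ambiguous and, taken literally, poorly matched to its hypothesis. It should be settled, but it does not threaten the trial's validity. The literal definition counts sensitisation that predates surgery and, when persistence is similar in the two arms, pulls the risk difference and risk ratio toward no effect. If new onset was meant, the defect is only the unstated link. If no randomised patient is sensitised at baseline, there is no numerical consequence.

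The size cannot be taken from the documents. At an assumed 20% baseline share, 22% new onset on-pump and full persistence, the loss is about 4 points of power at a risk ratio of 0.70 (14% to 10%) and 15 points at 0.50 (35% to 20%). Even with no baseline sensitisation, power is only 17% or 42%, so the outcome is underpowered under either definition, and correcting the wording will not change that.

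**What to change.** State that secondary outcome 3 is the LVAD-associated sensitization of the alloantibody section: cPRA above 10% at 30 days, 6 months and 12 months, compared by assigned arm among randomised patients not sensitised before implantation. Say openly that the baseline cut-off changes from below 10% to 10% or less, because a value of exactly 10% currently falls in neither category.

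Also report cPRA above 10% in all randomised patients, stratified by or adjusted for baseline cPRA status. This is an acceptable alternative as the main analysis. Which of the two has more power depends on persistence, which is unknown, so the choice must be made before outcome data by arm are seen.

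Restricting on baseline cPRA keeps the randomised comparison, because the value precedes the intraoperative randomisation. The cost is a few sentences of text and one further analysis, since pre-implant testing is already standard of care. The downsides are a smaller denominator for the restricted analysis (70 × 0.80 = 56 per arm at a 20% share), and any effect of technique on persistence is visible only in the all-patient analysis. The change does not settle how deaths or transplants before 6 or 12 months are handled, which is open under either definition.

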Patients undergoing implantation of CF-LVADs have a higher incidence of thrombotic and bleeding complications. Previous investigators found higher leukocyte counts, more neutrophil activation (28), and increased cytokine activation (29) in on-pump surgeries compared with off-pump cardiac surgeries. Recently, it was also demonstrated that the complement system is less activated by off-pump surgery (30). CPB activates platelets and coagulation factors, which causes impairment of hemostasis (31). The exact extent of hemostatic and fibrinolytic derangements in off-pump versus on-pump LVAD implantation is unknown.

Overall hemostasis potential (OHP) in plasma is a global functional test for assessing hemostatic potential and predicting clinical outcomes (bleeding, thrombosis). OHP in plasma is a newly developed laboratory method based on spectrophotometric measurement of the area under the curve for fibrin activation in citrated plasma samples (32). It is potentially useful for a rapid, and simple, bedside evaluation of patients with hemostatic dysfunction.

Other techniques for similar determinations, such as thromboelastography, require special equipment. With thromboelastography, the measurements should be performed on whole-blood samples within eight hours after sampling, and frozen samples cannot be used. Moreover, the observation time is up to several hours if the whole hemostatic process, especially the fibrinolysis part, is monitored. In contrast,

a global hemostatic assay for determination of overall hemostatic potential in plasma is inexpensive and relatively rapid. Estimation of OHP, coagulation, and fibrinolysis potential is finished in 40 minutes. With the exception of a common kinetic microplate reader, no special equipment is necessary for a global hemostatic assay. In addition, this technique is also useful for research purposes because frozen samples may be used.

There has not been a randomized study that has compared OHP in patients undergoing on-pump versus off-pump LVAD implantation. We speculate that with measurement of the OHP, it will be possible to better monitor the anticoagulant effects of antithrombotic drugs and prevent thrombotic and bleeding events. Further, by measuring the OHP, we might be able to stratify patients in different risk groups for thrombotic and bleeding complications.

Immunologic effects of LVAD after On-Pump versus Off-Pump LVAD implantation

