Per standard of care, every subject receives a **transthoracic echocardiogram (TTE)** within 48 hours prior to LVAD implantation (baseline). These preoperative echocardiograms are reviewed and compared with echocardiograms at 30 (+/- 5) days, 6-months and 1-year post-LVAD implantation. The echocardiograms will be performed by staff cardiologists at UTHealth/Memorial Hermann Hospital-TMC and are regularly scheduled per standard of care. The staff cardiologists will not be aware of the treatment assignment of enrolled patients.

For each subject, the following echocardiographic parameters will be pulled from the electronic medical record and transferred to case report forms:

- left ventricular end-systolic diameter (LVESD)
- left ventricular end-diastolic diameter (LVEDD)
- left ventricular (LV) ejection fraction
- severity of mitral regurgitation (MR) based on a graded system
- RV ejection fraction (RVEF),
- RV end-diastolic dimension (RVEDD),
- RV end-systolic diameter (LVESD)
- RV stroke work index (RVSWI),
- tricuspid annular plane systolic excursion (TAPSE)
- severity of tricuspid regurgitation (TR)

Right heart catheterization is another standard diagnostic procedure for LVAD patients. The test evaluates the hemodynamics of LVAD patients. Right heart catheter hemodynamic variables are analyzed pre-LVAD implantation and compared with 30 (+/- 5) days, 6-months and 1-year post-LVAD implantation values as regularly scheduled care. All procedures will be performed by staff cardiologists at UTHealth/Memorial Hermann Hospital-TMC, who will not be aware of the treatment assignments.

For each subject, the following hemodynamic measurements will be pulled from the electronic medical record and transferred to case report forms:

- central venous pressure (CVP),
- pulmonary artery pressures (PAP): systolic and diastolic PAP,
- pulmonary capillary wedge pressure (PCWP),
- cardiac index (CI)
- pulmonary vascular resistance (PVR)
- right-atrial pressure (RAP)
- RAP: pulmonary capillary wedge pressure (PCWP) ratio

Laboratory parameters: Per standard of care, blood for routine biochemical and coagulation markers will be taken at prior to surgery (within 48 hours) and at follow-up visits (30 days, 6 months, 1 year). The electronic medical record will be used to ascertain the results of the following laboratory tests:

- complete blood count
- blood glucose
- hemoglobin A1c
- total cholesterol
- LDL cholesterol
- HDL cholesterol
- triglycerides
- creatinine

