To evaluate the role of CPB on hemostatic and fibrinolytic parameters, we will make sure that the perioperative level of heparinization will be comparable between groups.

All patients will be postoperatively treated with 81mg aspirin daily and coumadin with a target international normalized ratio range of 2.0–2.5. Data on the use of antithrombotic therapy will be recorded at baseline and at each follow-up appointment. Time-in-Therapeutic Range (TTR) will be calculated using the Rosendaal method as a measure of quality of anticoagulation dose management (42).

Use of tranexamic acid

Tranexamic acid is a well-documented fibrinolytic inhibitor. The medical team will be advised to use always the same dose of tranexamic acid (if the patient's condition will allow it) in the perioperative period as it has an effect on overall fibrinolytic potential.

SELECTION OF SURGEONS

All surgical procedures will be performed by an "experienced" cardiac surgeon with more than 5 years of practice in cardiac surgery after residency training and has performed more than 100 LVAD implantations. Primary surgeons have experience with both techniques (on-pump and off-pump LVAD implantation). All procedures will be done under the supervision of an "expert" cardiac surgeon ([name]/PI of this protocol) who has more than 30 years of experience in advanced and complex cases of cardiac surgery, has performed more than 500 LVAD implantations, and is very experienced with both techniques (on-pump and off-pump LVAD implantation). Residents and fellows will not be eligible to participate as primary surgeons in the trial.

BLOOD COLLECTION AND PREPARATION

For research purposes, two additional vials of blood will be collected at the same time that standard of care blood draws are done. The timepoints for the research blood draws will be at baseline (within 48 hours of surgery), within 24-48 hours post-operation (but before discharge), 30 days, 6 months and 1 year. For the follow-up blood draws (+/- 5 days is acceptable).

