For the preparation of plasma, we will use vacutainer tubes with K2 EDTA. Each tube will be pre-labeled with patient's unique identifying number, patient's first and last name (two person-specific identifiers on the patient label) and date of blood draw from the subject. The collection tubes will be filled as defined by the manufacturer's package insert. Blood from tubes with reduced volume will not be processed. Immediately after filling each tube, the tube will be inverted 10 times gently (inversion can be performed while subsequent tubes are being filled). Blood tubes will stand at room temperature for approximately 30 minutes prior to centrifugation. Specimens will be processed and frozen within 2 hours of blood draw. Vacutainer tubes will be stored at 4-25°C (39-77°F) until processing. The study coordinator or other CAHF research staff will process the blood samples. Blood will spin in the centrifuge two times. First centrifugation will be used to separate plasma from white and red blood cells (RBCs). Whole blood will be centrifuged in the collection tubes for 12 minutes at 1500 x g, the temperature will be set to 4°C/39°F. The tubes will be removed from the centrifuge. If any of the Vacutainer tubes demonstrate gross hemolysis (bright red plasma), the tube will be discarded. After the first centrifugation, the buffy coat (containing leucocytes and platelets) will be visible as a very small whitish band above the RBCs. Using a disposable bulb pipette, plasma will be transferred from each collection tube to a 15 mL centrifuge tube. Centrifuge tubes will be placed in a centrifuge for a second time to remove any remaining cell debris that might contaminate the plasma sample. Plasma will be centrifuged for 12 minutes at 1500 x g. Using a clean disposable bulb pipette, plasma will be transferred from each centrifuge tube to a 15 mL pooling tube. A residual amount of plasma (≥ 0.5 mL; 12 mm or 1/2" in height) in the bottom of the centrifuge tube will be left in the centrifuge tube to avoid contamination with the pelleted cells. We expect to gain ~ 4 mL of plasma per Vacutainer tube. Plasma will be decanted into 1ml and 200ul aliquots in Eppendorf tubes. Plasma will be frozen in the pooling tubes upright in -80°C freezer until use. All used blood collection and processing tubes and pipettes will be discarded as biohazardous waste.

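### OHP is described as an assay on citrated plasma, but the only research plasma tube the protocol specifies is K2 EDTA

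*Combined protocol and SAP*

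**What the plan says.** The Background subsection on coagulation and fibrinolysis changes has the only description of the OHP assay. It presents OHP as a "spectrophotometric measurement of the area under the curve for fibrin activation in citrated plasma samples" and adds that frozen samples can be used for research.

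Under Study Design and Patients, "patients will be asked to provide additional blood samples for advanced hemostatic assays and panel reactive antibodies". The secondary hypothesis in the same section is that off-pump surgery "reduces OHP leading to lower complement activation and reduced immune allosensitization in the short term (30 days) and at long term (1 year"). Secondary outcome 5 is "OHP, overall coagulation potential and overall fibrinolytic potential in the perioperative period".

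Blood Collection and Preparation then sets the collection rule: "For research purposes, two additional vials of blood will be collected at the same time that standard of care blood draws are done". It lists five time points: baseline, 24-48 h after the operation, 30 days, 6 months and 1 year. It continues: "For the preparation of plasma, we will use vacutainer tubes with K2 EDTA". Spin, pooling and storage at -80°C follow for that plasma. No second tube type is mentioned.

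**The concern.** The assay and the collection rule name different specimens. The collection section is detailed: it fixes the anticoagulant, the number of inversions, spin force and time, temperature, pooling and storage. A coordinator who follows it would fill EDTA tubes, and the mismatch might surface only when the frozen plasma reaches the assay.

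At stake are secondary outcome 5 and the OHP part of the secondary hypothesis. By then the baseline and 24-48 h samples could not be collected again. The protocol takes care elsewhere to protect these measures, asking for comparable heparinization between arms and a uniform tranexamic acid dose. A specimen that does not match the assay would undercut that care.

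**Working it through.** The plan gives no figure to reproduce. The check compares the text and then counts the draws affected.

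**1. The two statements side by side**

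| Item | Where | What is given |
|---|---|---|
| OHP specimen | Background, coagulation-fibrinolysis subsection | Citrated plasma |
| Research plasma tube | Blood Collection and Preparation | K2 EDTA |
| Citrate tube | Whole document | None |
| OHP laboratory procedure, or OHP adapted to EDTA | Whole document | None |

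The word citrated appears only in the Background.

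**2. Is the research plasma the OHP plasma?** The collection section does not say so, but three points lead there. The extra blood is requested for hemostatic assays and PRA. The Background values OHP because it works on frozen samples, and this plasma is frozen until use. Determination of Alloantibodies takes alloantibody and PRA results from the medical record, so hemostatic assays are the clearest remaining purpose.

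**3. Could an unlisted citrate vial be among the two?** The section does not state that both vials are EDTA. It does name a single tube type for plasma, and OHP is a plasma assay. It also directs that "plasma will be transferred from each centrifuge tube to a 15 mL pooling tube", so a citrate tube would have no separate path.

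**4. Could routine blood fill the gap?** Under the laboratory parameters, blood for biochemical and "coagulation markers will be taken at prior to surgery (within 48 hours) and at follow-up visits (30 days, 6 months, 1 year"). Only results are transferred from the record. No routine plasma is kept for research, and no coagulation draw is listed at 24-48 h.

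**5. Count of draws**

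Inputs: 140 patients (Statistical Methods) and 5 research draws each (Blood Collection and Preparation). The counts are maxima, assuming no deaths, missed draws or loss to follow-up.

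- All research draws: 140 × 5 = 700.
- Outcome 5, reading perioperative as baseline plus 24-48 h: 140 × 2 = 280, and 280/700 = 40%.
- Adding 30 days and 1 year from the secondary hypothesis: 140 × 4 = 560, and 560/700 = 80%.
- The 6-month draw (140) is named by no OHP outcome or hypothesis.
- Perioperative draws with no routine coagulation draw listed at that time (24-48 h): 140 × 1 = 140 of 280.

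**The case against.** The strongest reply is that the conflict depends on a link the protocol never states. The Background describes a published method, the collection section does not mention OHP, and that section also banks buffy coat and red cells. It could describe general banking, with the OHP tube simply left out. That is possible, but it does not rescue the plan. On that reading, secondary outcome 5 has no specified specimen at all, and the same correction is needed.

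Other objections limit the size of the point:

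- **Time points.** In the secondary hypothesis, 30 days and 1 year may attach to allosensitization and not to OHP. Equating perioperative with baseline plus 24-48 h is also an inference, because the protocol does not define the term. This stands, so 40% to 80% is a range that depends on reading. It counts planned draws and does not measure bias or lost information.
- **Fallback at 24-48 h.** Research vials are drawn alongside standard-of-care blood, so some routine blood is taken then, and INR monitoring goes beyond the listed laboratory schedule. This also stands in part. The 140 figure means only that no coagulation draw is listed at that point. It does not mean that the other 140 have a usable fallback, since routine plasma is not retained at any time.
- **EDTA might work.** The documents do not rule this out. They also offer no method for it.

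**Conclusion.** The concern holds. The collection rule and the protocol's only description of the OHP assay conflict, and nothing else in the document resolves it. Followed as written, the plan stores plasma that does not match the assay for secondary outcome 5 and for the OHP part of the secondary hypothesis.

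The mismatch itself is certain from the text. Its consequence for the outcome is less so: it rests on the research plasma being the OHP specimen, which is evident but not stated. No claim is made that OHP cannot be measured in EDTA plasma.

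The primary composite is unaffected. The allosensitization outcome is not touched by the mismatch either, because its data come from the medical record. This should be fixed before samples are collected, but it does not threaten the main comparison.

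**What to change.** In Blood Collection and Preparation, state that at baseline, 24-48 h, 30 days and 1 year at least one of the two research vials will be a citrate tube. Its plasma should be processed, pooled, labelled and stored apart from EDTA plasma, and OHP and its two component potentials should be measured only on it. The documents say only citrated, so the OHP laboratory should name the exact tube. It should also confirm whether the present spin, pooling and freezing steps suit the assay; they should not be carried over by default.

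Alternatively, describe an OHP method for EDTA plasma, validate it before use, and amend the Background to match. If any EDTA samples have already been stored, OHP results from them should be excluded or reported separately.

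The citrate route costs a tube specification, a label, a separate pooling step and laboratory wording. It adds no draw but reduces the EDTA bank. Assuming both vials are now EDTA and each yields the protocol's approximate 4 mL of plasma:

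- Now: 5 × 2 × 4 = 40 mL per patient.
- One vial changed at four time points: 40 - 4 × 4 = 24 mL (-40%).
- One vial changed at baseline and 24-48 h only: 40 - 2 × 4 = 32 mL (-20%).

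Study Design and Patients also gives PRA as a use of the extra blood, so confirm that the remaining vial is enough for it. The EDTA route costs a validation study instead.
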